9.1 EFFICACY ASSESSMENTS

We will assess the feasibility and preliminary efficacy of MMF's ability to safely attenuate immunogenicity conferred by pegloticase as determined by the proportion of participants randomized to peg + MMF achieving and maintaining an $sUA \le to 6$ mg/dL through 12 weeks (Visit 11), compared to concurrent controls (peg + PBO). After 12 weeks of coadministration of MMF or PBO, all participants will continue on pegloticase for an additional 12 weeks without combination therapy to determine the durability of immune modulation by assessing the absolute change in sUA from baseline to Week 24 (Visit 17), change in sUA from Week 12 (Visit 11) to Week 24 (Visit 17), and to determine the proportion of participants with $sUA \le 6$ mg/dL through Week 24 (Visit 17), and Week 12 (Visit 11) to Week 24 (Visit 17). Samples will be drawn for laboratory assessment at Visits 1-17 and at unscheduled visits. At visits 18-20 specimen samples will be collected for assessment of anti-pegloticase antibodies.

9.2 SAFETY AND OTHER ASSESSMENTS

Physical examination: A complete physical examination (e.g., height and weight, organ systems, motor or vision assessment, or other functional abilities) will be performed at Visit 1, Visit 11, and Visit 17. and targeted physical examination with joint assessment will be performed at Visit 3, 5, 7-10, 1217.

Vital signs: consisting of heart rate, respiratory rate, blood pressure (noting the position in which it was obtained), and body temperature will be performed at Visit 1, 2, 3, 5, 7-17.

Biological specimen collection: Following Screening Visit, Visits 3, 8, 11, 14, 17-20, and any unscheduled visits a biospecimen will be collected for measurement of antibody response. Additionally, in the event a participant experiences an infusion reaction during a specimen will be collected, as high titer anti-pegloticase antibodies have been associated with a loss of responsiveness to pegloticase and increased infusion reactions.

Assessment of study intervention adherence: Infusion logs and pill counts (during the first 12 weeks) will be kept measure participant adherence to the study intervention.

Assessment of adverse events: Significant findings that occur after administration of pegloticase which meet the definition of an AE will be recorded in the medical record and on the Adverse Events care report forms.

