 - Medication history (including use of over-the-counter medications [eg. aspirin], use of other prescription medications including gout medications)
 - Dietary supplement/vitamin use
- Vital signs
- Physical exam includes, but is not limited to
 - Eye, Head, Ears, Nose, and Throat Exam (HEENT), and Neck
 - Cardiovascular
 - Dermatological

- Respiratory
- Gastrointestinal
- Musculoskeletal
- Neurologic
- Integumentary
- VS/Measurements
- Gout Flare/ assessment
- o PROs (eg. PROMIS-29 & GIS instrument)
- Blood draw
- Screening Visit Laboratory
 - CBC with diff
 - HIV1 and 2 Antibody Screen
 - IgG
 - sUA
 - Pregnancy test for premenopausal women
 - Comprehensive Metabolic Panel (CMP)
 - G6PD
 - Specimen collection (blood sample for serum banking)
 - Pegloticase Antibody/Mechanistic Study

Vital signs will consist of heart rate, respiratory rate, blood pressure (noting the position in which it was obtained), and body temperature (taken either orally or aurally). All measurements of pulse rate and blood pressure should be made after approximately 5 minutes of rest. Focused history and physical examination: Information collected will include date of birth, self-reported race/ethnicity (defined as in previous studies investigating its role in rheumatic diseases, gout history, medication history (including use of aspirin, gout medications), weight, and height. Assessments for presence of tophi will be conducted as well as gout history and symptom severity.

- Document the number of gout flares in the last 6 months and 12 months and the most recent occurrence. Patients with gout flares can enter the study if the flare treatment is discontinued 1 week prior to the first dose of pegloticase.
- o Document the presence and/or history of gout-related kidney disease.

Physical examinations will be performed by body system at Screening, Visit 11, and Visit 17 (end of treatment) or early termination visit in the pegloticase dosing phase. Significant findings prior to the administration of pegloticase must be recorded in the patient's medical record and included on the Medical History in the eCRFs. Significant findings that occur after administration of pegloticase which meet the definition of an AE must be recorded in the medical record and on the Adverse Events eCRF page.

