All women of childbearing potential must use an effective form of birth control during this study and for 30 days after completion of the study. Acceptable methods of birth control include hormonal control methods, inter-uterine device, a double-barrier method (diaphragm with spermicide, condom with spermicide) or abstinence. All male participants will be cautioned to use proper birth control methods with their partners during the course of the study in which MMF is received.³

Laboratory: sUA, CMP, CBC with diff, and pregnancy test for premenopausal women. Additionally, a sample will be collected at screening, Visits 1, 8, 11, 14, and 17-20 for evaluation of anti-pegloticase Ab. Serum samples (see **Appendix 5)** will be collected and prepared for transport to the clinical research lab in the Division of Clinical Immunology and

Rheumatology at the University of Alabama at Birmingham. All lab samples will be discarded if the participant is deemed not eligible for the study.

Visit 2 - Run-In Visit

- Obtain and record vital signs, including pulse rate, sitting blood pressure, and body temperature
- Review / update concomitant medications
- Gout Flare/tophus assessment
- o Blood draw
- Laboratory
 - sUA
 - Urine pregnancy test for premenopausal women
 - CMP
- Randomization will occur at Visit 2/Run-In. Dispense 2 week course of MMF (500mg/twice per day for the first week, and 1000mg/twice per day for the second week of run-in) or placebo, with dosing instructions per randomization assignment.
- Gout Flare Prophylaxis

Participants will be placed on a prophylactic regimen of colchicine or NSAID to prevent gout flares, unless medically contraindicated or not tolerated, and will receive this prophylaxis for at least two weeks prior to the first administration of pegloticase. Gout flare prophylaxis will continue for the duration of the study unless medically contraindicated or not tolerated.

Visit 3 (Baseline-0 weeks)

Visit 3 will occur within 2 weeks of the run-in visit.

The markers for the study primary and secondary outcomes will be collected at each visit. Other data will be collected as needed for safety monitoring.

- Obtain and record vital signs, including pulse rate, sitting blood pressure, and body temperature
- Review / update concomitant medications
- Assess any AEs, and record
- Gout Flare assessment
- Assess compliance (via pill count) and dispense course of MMF (1000 mg/twice per day) or PBO, with dosing instructions

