9.3 ADVERSE EVENTS AND SERIOUS ADVERSE EVENTS

9.3.1 DEFINITION OF ADVERSE EVENTS (AE)

Adverse event means any untoward medical occurrence associated with the use of an intervention in humans, whether or not considered intervention-related (21 CFR 312.32 (a)).

This is a Phase II, double-blind, placebo controlled examining two medications (pegloticase and MMF) that are already FDA approved and have been in clinical use for over 5 years, but are not commonly co-administered. Any worsening (i.e. any clinically significant adverse change in frequency or intensity) of a preexisting condition which is temporally associated with the use of pegloticase or MMF is also considered an AE. Abnormal laboratory values or test results will constitute AEs if they differ significantly from baseline, and will be recorded in the CRF. Screening conditions will not be considered AE; however, worsening of a preexisting condition may be considered an AE. We will start collecting AEs at Visit 3. All AE and SAE's will be able to be reviewed electronically via the eDES and electronic medical record.

The safety events of interest in assessing study risks and benefits are IRs and a co-primary study outcome. Participants will be followed for the occurrence of IR and secondary outcomes of interest events at each study visit. Supplementing the data collected during these visits will be information collected regarding participant reported health-related quality of life (QOL), and for improved, near real-time assessment of outcome events. Non-serious events that are expected according to previous experience with the study drugs (pegloticase, MMF) as described in the protocol, consent materials, or any approved product labelling will also be collected. We will report all serious AEs according to appropriate authority (e.g., NIAMS, FDA, IRB) in compliance with guidelines and regulations.

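### The protocol contradicts itself on when adverse-event recording starts and leaves the laboratory baseline unnamed, so non-serious MMF effects in the run-in could be left out of the co-primary safety result

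*Combined protocol and SAP*

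**What the plan says.** **Start of randomised drug.** In section 9, randomisation and dispensing take place at Visit 2: "Dispense 2 week course of MMF (500mg/twice per day for the first week, and 1000mg/twice per day for the second week of run-in". The first infusion follows at the next visit: "Visit 3 will occur within 2 weeks of the run-in visit".

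**Rules that start AE recording at pegloticase or Visit 3.**
- Section 9.2, in its paragraph on AEs: "Significant findings that occur after administration of pegloticase which meet the definition of an AE will be recorded".
- Section 9, Visit 1, in the paragraph on physical examinations, has a separate rule for earlier findings: "Significant findings prior to the administration of pegloticase must be recorded in" the participant's chart. Such findings are also to be "included on the Medical History in the eCRFs".
- Section 9.3.1: "We will start collecting AEs at Visit 3". The schedule of activities (section 2.3) also has its first AE assessment at Visit 3.

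**Rules that start earlier.**
- Section 9.3.4 records reportable events with onset at any time from informed consent, with a separate end date for non-serious events. It documents all AEs that occur on study drug, asks at each visit about events since the previous one, and treats conditions present at screening as baseline.
- Section 8.1 makes any new clinically relevant finding after enrollment an AE.
- Section 9.3.3.2 monitors serious events from enrollment.

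**Laboratory baseline.** Section 9.3.1: "Abnormal laboratory values or test results will constitute AEs if they differ significantly from baseline". No visit is named. Visit 3 is headed "Visit 3 (Baseline-0 weeks", and the blood-pressure exclusion in section 6.2 applies the word baseline to both Visit 1 and Visit 3.

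**Analysis set.** Section 10.3 defines mITT by at least one dose of MMF or placebo in the treatment period, without saying whether the run-in belongs to it.

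**The concern.** Safety is a co-primary aim. The synopsis frames it as events potentially associated with MMF, and sections 10.4.1 and 10.4.2 make a recommendation for a full-scale trial conditional on safety. Two weeks of MMF exposure, including the step from 500 mg to 1000 mg twice daily, come before the point at which three parts of the protocol begin AE recording. This is when early intolerance would show, and tolerability in that window governs the dose.

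Two sites could each follow the protocol and file the same run-in event differently, one as an AE and the other as medical history. MMF-caused events can arise only in the MMF arm, so leaving them out would make MMF look safer than it is. With 24 and 8 participants and a descriptive safety analysis, one or two misfiled cases are visible in the result.

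The unnamed laboratory baseline carries a similar risk. Section 9.3.3.3 lists leukopenia, thrombocytopenia and raised transaminases among the expected MMF effects. If change is measured from Visit 3, whatever happened in the run-in is already inside the reference value.

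**Working it through.** The plan gives no figure on this point, so there is none to reproduce. The check is a comparison of sections, followed by an illustration of scale.

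**Step 1. A non-serious event that starts in the run-in (for example, diarrhea on day 5 of MMF).**

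| Section | Treatment of the event |
|---|---|
| 9.2 | Describes AE recording only from pegloticase on; silent on earlier findings |
| 9, Visit 1 | Medical history, if read as applying beyond scheduled examinations |
| 9.3.1 | Collection begins at Visit 3; onset before that is not addressed |
| 9.3.4 | AE: onset after consent, on study drug, within the Visit 3 look-back |
| 8.1 | AE: new clinically relevant finding after enrollment |

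Section 9.3.1 alone is compatible with capture, because Visit 3 asks about the time since Visit 2. Read with 9.2 and the Visit 1 text, it supports leaving the event out. No section states an order of precedence. Serious events do not depend on this (9.3.3.2).

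**Step 2. Laboratory values.** From the schedule in section 2.3:
- CBC: Visits 1 and 3, none at Visit 2.
- IgG: Visits 1 and 3.
- CMP: Visits 1, 2 and 3.

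The first CBC after screening therefore follows up to 14 days of MMF. Values from before MMF exist for every safety laboratory, so a clean baseline is available if it is named.

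**Step 3. Share of exposure.**
- Days: run-in 14; Weeks 0 to 12, 84; 14/(14 + 84) = 14.3%.
- Dose: 7 × 1 g + 7 × 2 g = 21 g; 21 + 84 × 2 = 189 g; 21/189 = 11.1%.

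**Step 4. Illustrative loss.** Inputs: 24 MMF participants (section 5.1); leukopenia 28%, a rheumatoid arthritis figure (9.3.3.3); neutropenia 3.6%, the upper end of 2% to 3.6% (3.3.1). The share of first onsets that falls in the run-in is not given. Even onset gives 14.3%; 5% and 50% are shown as an assumed range. Every run-in case is taken as lost and not recorded later.

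Cases missed = 24 × rate × share. Reported rate = rate × (1 − share). Chance that at least one is missed = 1 − (1 − rate × share)^24.

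| | Expected cases | Missed at 5% / 14.3% / 50% | Reported rate |
|---|---|---|---|
| Leukopenia, 28% | 24 × 0.28 = 6.72 | 0.34 / 0.96 / 3.36 | 26.6% / 24.0% / 14.0% |
| Neutropenia, 3.6% | 24 × 0.036 = 0.86 | 0.04 / 0.12 / 0.43 | 3.4% / 3.1% / 1.8% |

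At the even-onset share, the chance of missing at least one case is 1 − (1 − 0.04)^24 = 62% for leukopenia and 1 − (1 − 0.00514)^24 = 12% for neutropenia. A constant hazard over 14 weeks, 24 × (1 − (1 − rate)^(2/14)), gives nearly the same counts: 1.10 and 0.13.

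**The case against.** The strongest reply is that the protocol already captures these events. Section 9.3.4 is the section that governs the time period. It runs from consent, covers non-serious events explicitly and includes everything on study drug. Section 8.1 adds any new clinically relevant finding after enrollment. Visit 3 assesses AEs with a look-back over the run-in. Much of this stands, and it rules out several stronger readings that a reader might infer:

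- *That the protocol excludes run-in events.* It does not. Section 9.2 says what will be recorded after pegloticase; it does not say that earlier findings are to be left out. The medical-history sentence sits in a paragraph on body-system examinations at screening, Visit 11 and Visit 17, none of which falls in the run-in.
- *That baseline means Visit 3.* For medical conditions it is screening (9.3.1, 9.3.4). For laboratory values it is undefined, and nothing fixes it at Visit 3.
- *That any drug-caused change in the run-in belongs to the MMF arm.* Colchicine or NSAID prophylaxis also starts at Visit 2, in both arms. Diarrhea (23%) and, rarely, neutropenia are expected with colchicine (9.3.3.3). Only MMF-caused events are specific to the MMF arm.
- *That a participant who stops MMF before any infusion drops out of the safety record.* Sections 8.1 and 9 provide follow-up after study drug is discontinued, and withdrawal due to AEs is a listed safety endpoint (section 4).

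Appendix 9 and the manual of procedures are not among the documents and may hold the operative instruction. What the reply does not do is say which rule prevails where the sections conflict, or name the laboratory baseline.

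**Conclusion.** The concern holds as an internal contradiction on the start of AE recording, together with an undefined laboratory baseline. A site that follows 9.2, the Visit 1 text and 9.3.1 could leave non-serious run-in events, including MMF intolerance, out of a co-primary result; a site that follows 9.3.4 and 8.1 would not. Serious events are not affected.

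The documents do not show that data will be lost, and the size of any loss cannot be determined from them. About 1 of 6.7 leukopenia cases, or about 0.1 neutropenia case, is what follows if onset is even and every run-in case goes unrecorded. It is an illustration under a pessimistic capture assumption and not an estimate. The leukopenia rate also comes from another disease. The point should be corrected because the fix is cheap and MMF safety is what the trial is meant to describe.

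**What to change.** 1. Align section 9.2, the Visit 1 text and section 9.3.1 with 9.3.4: AEs, including laboratory AEs, count from the first dose of MMF or placebo. Have Visit 3 ask explicitly about the run-in, and flag each onset as before or after the first infusion so that pegloticase-related events stay identifiable.
2. Define the safety-laboratory baseline as the last value before the first MMF/placebo dose: Visit 1 for CBC and IgG, Visit 2 for CMP. State that the Visit 3 heading does not set this baseline, and use the same values for the laboratory rows in section 10.4.4.
3. State in section 10.3 that the mITT treatment period includes the run-in.

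The cost is wording. All samples are already scheduled, so there are no new visits or draws. The downside is a few more low-grade events to record. By-arm tables of laboratory change and shift from the new baseline would be useful but are optional in a pilot whose safety analysis is declared mostly descriptive.

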9.3 ADVERSE EVENTS AND SERIOUS ADVERSE EVENTS

9.3.1 DEFINITION OF ADVERSE EVENTS (AE)

Adverse event means any untoward medical occurrence associated with the use of an intervention in humans, whether or not considered intervention-related (21 CFR 312.32 (a)).

This is a Phase II, double-blind, placebo controlled examining two medications (pegloticase and MMF) that are already FDA approved and have been in clinical use for over 5 years, but are not commonly co-administered. Any worsening (i.e. any clinically significant adverse change in frequency or intensity) of a preexisting condition which is temporally associated with the use of pegloticase or MMF is also considered an AE. Abnormal laboratory values or test results will constitute AEs if they differ significantly from baseline, and will be recorded in the CRF. Screening conditions will not be considered AE; however, worsening of a preexisting condition may be considered an AE. We will start collecting AEs at Visit 3. All AE and SAE's will be able to be reviewed electronically via the eDES and electronic medical record.

The safety events of interest in assessing study risks and benefits are IRs and a co-primary study outcome. Participants will be followed for the occurrence of IR and secondary outcomes of interest events at each study visit. Supplementing the data collected during these visits will be information collected regarding participant reported health-related quality of life (QOL), and for improved, near real-time assessment of outcome events. Non-serious events that are expected according to previous experience with the study drugs (pegloticase, MMF) as described in the protocol, consent materials, or any approved product labelling will also be collected. We will report all serious AEs according to appropriate authority (e.g., NIAMS, FDA, IRB) in compliance with guidelines and regulations.

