9.3.4 TIME PERIOD AND FREQUENCY FOR EVENT ASSESSMENT AND FOLLOW-UP

The occurrence of an adverse event (AE) or serious adverse event (SAE) may come to the attention of study personnel during study visits and interviews of a study participant presenting for medical care, or upon review by the study monitor (see section 11.1.7).

All AEs including local and systemic reactions not meeting the criteria for SAEs will be captured on the appropriate case report form (eCRF). Information to be collected includes event description, time of onset, clinician's assessment of severity, relationship to study drug (assessed only by those with the training and authority to make a diagnosis), and time of resolution/stabilization of the event. All AEs occurring while on study drug will be documented appropriately regardless of relationship. All AEs will be followed to adequate resolution.

Any medical condition that is present at the time that the participant is screened will be considered as baseline and not reported as an AE. However, if the study participant's condition deteriorates at any time during the study, it will be recorded as an AE.

Changes in the severity of an AE will be documented to allow an assessment of the duration of the event at each level of

severity to be performed. AEs characterized as intermittent require documentation of onset and duration of each episode.

The study coordinator will record all reportable events with start dates occurring any time after informed consent is obtained until 7 (for non-serious AEs) or 30 (for SAEs) days after the last day of study participation. At each study visit, the investigator will inquire about the occurrence of AE/SAEs since the last visit. Events will be followed for outcome information until resolution or stabilization.

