10.3 POPULATIONS FOR ANALYSES

The analysis population will include all enrolled participants who received at least 1 dose of study medication (mycophenolate mofetil or placebo) during treatment period (modified intention to treat, mITT). The protocol

population will be all participants who attend all study visits and complete the trial.

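### Adverse event recording starts at informed consent in 9.3.4 but at Visit 3 or after pegloticase in 9.3.1 and 9.2, so non-serious events in the MMF/placebo run-in may be lost

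*Combined protocol and SAP*

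**What the plan says.** The protocol gives more than one starting point for AE recording.

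- **9.3.1:** "We will start collecting AEs at Visit 3". The same section undertakes to collect "Non-serious events that are expected according to previous experience with the study drugs (pegloticase, MMF) as described in the protocol" and other listed sources, without saying from when.
- **9.2:** "Significant findings that occur after administration of pegloticase which meet the definition of an AE will be recorded". The first infusion is at Visit 3.
- **2.3 Schedule of Activities:** the first mark in the AE row is at Visit 3. The footnote to that row cannot be read in the text available, so the table carries little weight alone.
- **9.3.4:** reportable events are those with "start dates occurring any time after informed consent is obtained until 7 (for non-serious AEs) or 30 (for SAEs) days" after participation ends. It adds "All AEs occurring while on study drug will be documented appropriately regardless of relationship", and on method: "At each study visit, the investigator will inquire about the occurrence of AE/SAEs since the last visit".

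Study drug starts before Visit 3. Under Visit 2 in section 9: "Randomization will occur at Visit 2/Run-In. Dispense 2 week course of MMF" or placebo. The analysis population in 10.3 follows that first exposure: "all enrolled participants who received at least 1 dose of study medication (mycophenolate mofetil or placebo"). Neither the endpoint in section 4 nor its analysis in 10.4.3 says when the AE window opens.

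**The concern.** Sites can follow different sections in good faith. One that works from 9.3.4 records nausea on day 3 of the run-in. One that works from 9.2, or reads 9.3.1 literally, need not.

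Early MMF events are of direct interest here. The Synopsis directs the second co-primary aim at events potentially associated with MMF. Sections 10.4.1 and 10.4.2 make a recommendation for a full-scale trial conditional on safety. The version 6.0 entry in 11.4 explains the run-in titration as a way to find MMF intolerance sooner. A participant who takes MMF in the run-in and stops before any infusion counts in the mITT denominator, but under the literal wording the AE behind that decision might not be recorded as one.

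**Working it through.** **1. The passages side by side**

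| Section | AE window opens | Covers a non-serious event in the run-in? |
|---|---|---|
| 9.3.4 | Informed consent; all AEs on study drug | Yes |
| 9.2 | After pegloticase (Visit 3) | Not as worded |
| 9.3.1 | Visit 3 | Not if read literally; yes if Visit 3 is only the first time of asking |
| 2.3 Schedule | First mark at Visit 3 | As 9.3.1 |

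The consent-to-follow-up sentence in 9.3.4 gives an end date for non-serious AEs, so it is not confined to serious ones. The clearest conflict is 9.2 against 9.3.4, because 9.2 sets its limit by when the finding occurs, not by when the question is asked.

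**2. Size of the window**

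The plan states no figure to reproduce. Inputs: a 2-week run-in (500 mg twice daily for one week, then 1000 mg twice daily for one week), 12 further weeks at 1000 mg twice daily, and 24 participants on MMF (7.3).

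- Share of time: 2/(2 + 12) = 14.3%; that is 24 × 2 = 48 of 24 × 14 = 336 participant-weeks.
- Share of scheduled dose: (7 × 1 g + 7 × 2 g)/(7 × 1 g + 7 × 2 g + 84 × 2 g) = 21/189 = 11.1%.

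**3. Illustration of events at risk**

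Section 3.3.1 gives 36% for persistent diarrhoea and 20% for nausea; 9.3.3.3 gives 12% for nausea and vomiting. Assume that these rates apply over the 14 weeks and that onset is proportional to dose (lower figure) or time (upper figure). Run-in onsets = 24 × rate × share:

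- Diarrhoea: 24 × 0.36 × 0.111 = 0.96 to 24 × 0.36 × 0.143 = 1.23
- Nausea at 20%: 24 × 0.20 × 0.111 = 0.53 to 24 × 0.20 × 0.143 = 0.69
- Nausea at 12%: 24 × 0.12 × 0.111 = 0.32 to 24 × 0.12 × 0.143 = 0.41

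Only events that resolve before Visit 3 and do not recur would be missed. Call that share q; the documents do not give it.

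| q | Diarrhoea (36%) missed | Nausea (20%) missed |
|---|---|---|
| 0 | 0 | 0 |
| 25% | 0.24–0.31 | 0.13–0.17 |
| 50% | 0.48–0.62 | 0.27–0.34 |
| 100% | 0.96–1.23 | 0.53–0.69 |

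For diarrhoea described as persistent, q is probably low.

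**4. Sensitivity to early onset**

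If intolerance clusters at the start of treatment, proportional onset understates the run-in share. Let s be the assumed share of all cases that both begin and resolve in the run-in. At s = 5%, 24 × 0.36 × 0.05 = 0.4 diarrhoea cases and 24 × 0.20 × 0.05 = 0.2 nausea cases would be missed. At s = 50%, the figures are 4.3 and 2.4. The documents do not support any particular value. For scale, one participant in 24 is 4.2 percentage points.

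**The case against.** The strongest reply is that the sections can be read together. Visit 3 is the first listed visit after study drug is dispensed, its procedures include AE assessment, and 9.3.4 requires each visit to ask about the interval since the previous one. No study drug has been taken by Visit 2, so the absence of an AE assessment there is unremarkable. Section 9.2 does not say that only post-pegloticase findings are recorded, and 9.3.4 treats only conditions present at screening as baseline. This reading is reasonable for 9.3.1 and the Schedule, but 9.3.1 does not state it. It does not explain why 9.2 uses pegloticase as its cut-off when another study drug started earlier.

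Other safeguards also stand. Section 9.3.3.2 starts monitoring at enrolment in its paragraph on serious events, 8.2 records reasons for withdrawal, and section 9 keeps collecting data after drug discontinuation, with AE assessment at Visits 17 to 20 and laboratory tests repeated at Visit 3. The safety analysis is mostly descriptive, and the same rule applies to both blinded arms. The lower nausea rate in 9.3.3.3 reduces the illustration further. The manual of procedures and Appendix 9, which were not available, may settle the start date. These points limit the effect; they do not remove the inconsistency from the protocol text.

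**Conclusion.** The concern holds. Section 9.2 conflicts with 9.3.4 on when AE recording begins; 9.3.1 and the Schedule do so if read literally, and no section reconciles them. The exposure affected is at most 2 of 14 MMF weeks. The risk is confined to non-serious events that begin and resolve in the run-in without recurring. With onset proportional to time or dose, that is from zero to about one participant in 24 for diarrhoea and fewer for nausea. It would be more if onset is concentrated early. The wording mismatch is certain; the number of events lost is unknown. It should be fixed because it concerns the start of a co-primary endpoint window and is easily corrected.

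**What to change.** State that 9.3.4 governs. In 9.3.1, replace the Visit 3 start with informed consent and say that the Visit 3 assessment covers the run-in. In 9.2, refer to the first dose of any study drug instead of pegloticase. In 10.4.3, count treatment-emergent AEs from the first MMF/placebo dose over the mITT denominator, and flag events between consent and that dose so that they are reported separately.

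Three clarifications in related text are useful but secondary:

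- The Visit 1 physical-examination paragraph uses pegloticase as the cut-off between medical history and AE; refer to first study drug.
- The minimum data set for consented participants who never received pegloticase should not replace AE recording for anyone who took MMF/placebo. The follow-up text in section 9 suggests this is already intended.
- Laboratory AEs are judged against a baseline that is not named, and Visit 3 is itself labelled baseline. Name the last value before the first MMF/placebo dose; per the Schedule, that is Visit 1 for the CBC and Visit 2 for the CMP.

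The cost is protocol and minor eCRF wording plus one flag in the data, with no new visit or procedure. Reported AE rates may rise slightly.
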